6.3 Labeling

rF1V vaccine and CpG 1018 adjuvant solution will be provided for the study and labeled for clinical study use.

At a minimum, both rF1V vaccine and CpG 1018 adjuvant solution will be labeled with the following information: product name, product lot number, contents, volume, concentration, sponsor name, and a statement indicating that the drug is for investigational use only.

6.4 Storage and Handling Instructions

The clinical supplies storage area at the site must be monitored closely by the designated site staff for temperature consistency and documentation of temperature monitoring must be maintained. Temperature excursions outside of the recommended storage range may impact product quality and must be reported to Dynavax or its designee per the detailed instructions in the Pharmacy Manual.

6.4.1 rF1V and CpG 1018

Both rF1V vaccine and CpG 1018 must be kept under refrigeration (2°C to 8°C). After preparation of drug product, it must be used within 6 hours.

Do not freeze. If product is frozen, do not use. A Pharmacy Manual will be provided with specific instructions for management of temperature excursions.

6.4.2 Bedside mix of rF1V vaccine and CpG 1018

Please refer to the Pharmacy Manual for additional information.

7 TREATMENT OF SUBJECTS

7.1 Study Treatments

Study treatments are presented in [Table 7-1](#). For each dose, injections are to be administered in the order specified in the table.

Table 7-1: Study Treatments

A 10x10 grid of black rectangles on a white background. The grid is composed of 100 individual rectangles. A central column of 10 rectangles is located in the middle of the grid, and a central row of 10 rectangles is located in the middle of the grid. The rectangles are arranged in a staggered pattern, with some rectangles overlapping others. The grid is composed of 100 individual rectangles.

7.2 Dosage and Dosage Regimen

Subjects will receive their assigned vaccine on Day

7.3 Treatment Compliance

All study injections will be administered by the designated unblinded study personnel only.

7.4 Control and Accountability of Investigational Medicinal Product

All investigational medicinal product (IMP) must be received by a trained designated person at the study site, handled and stored safely and properly, and kept in a secured location with limited access.

The investigator (or responsible designee) must maintain current and accurate records of the receipt (documentation from shipments of study treatments received), administration (by subject and overall accounting) and return of study treatments to a Dynavax-specified facility for destruction (or destroyed by procedures approved by Dynavax). All study treatments must be stored in a location with access restricted to authorized personnel only.

A study monitor will be responsible for monitoring the drug accountability at the site. The study monitor should be contacted with any questions concerning administration of study treatments.

Records of study treatment accountability, storage, and handling must be made available to the study monitor for the purposes of study treatments accountability. Any discrepancy and/or deficiency must be recorded with an explanation.

Unless superseded by Standard Operating Procedures (SOPs), the investigator must retain all used vials, expired vials, damaged vials, and unused vials of study vaccine until accountability has been confirmed by the study monitor. Any exceptions to this policy must be specifically granted by Dynavax or its designee.

At the end of the study, or upon request by Dynavax, all used, partially used, and unused study treatments must be destroyed by procedures approved by Dynavax or returned to a Dynavax-specified facility for adequate disposition.

Refer to the Pharmacy Manual for detailed instructions on handling, control, and accountability of study vaccine.

Study vaccine may not be used for any purpose other than that described in this protocol.

7.5 Concomitant Medications

7.5.1 Prohibited Treatments or Therapies

The following non-study medications are prohibited:

- **Any licensed COVID-19 vaccine or inactivated vaccine (including vaccines containing mRNA or CpG)**
 - :S 14 days prior to each study injection through 14 days after each study injection
- **Any live vaccine**
 - :S 28 days prior to each study injection through 28 days after each study injection

- **Other concomitant medications**

- :S 28 days prior to vaccine injection (Day 1) through 28 days after the third study vaccine injection Week 26 (Day 183):
 - Systemic corticosteroids (more than 3 consecutive days) or other immunomodulators or immunomodulators immune suppressive medication, with the exception of inhaled steroids
 - Any other investigational medicinal agent
- :S 90 days prior to vaccine injection (Day 1) and through 28 days after the third study vaccine injection Week 26 (Day 183):
 - Granulocyte or granulocyte-macrophage colony-stimulating factor
 - Immunoglobulins or any blood products
 - Antisense oligonucleotides
 - Drugs/investigational agents with very long half-lives (defined as 2' 60 days)
- At any time prior to vaccine injection (Day 1) and through 28 days after the third study vaccine injection Week 26 (Day 183):
 - DNA plasmids or other genetic therapy intended to integrate permanently into host cells

If a subject requires treatment that is prohibited, **the subject will not be withdrawn from the study** but will be followed for safety through Week 56.

7.5.2 Permitted Therapy

Use of any permitted medications, including over-the-counter medications or vaccine(s) during the 28 days prior to the first study vaccine injection through Week 56 or Early Discontinuation/EOS Visit, should be solicited from each subject and recorded in source documents. Use of vitamins and dietary supplements will not be collected. Medications started prior to dosing, and any medication used within the 28 days prior to dosing will be recorded.

All collected concomitant medications will be recorded in the CRF.

8 MANAGEMENT OF SUBJECT SAFETY

8.1 Data Monitoring Committee

The Sponsor will establish a DMC for this study. The DMC members and procedures will be described in the DMC charter.

8.2 Potential Reasons for Stopping the Study

Dosing of all subjects will be temporarily stopped for any of the following:

- Two or more subjects with Grade 3 (severe) or higher severity solicited adverse reactions (considered by the sponsor to be possibly or probably related to treatment) lasting more than 48 hours AND considered by the DMC to be clinically significant
- Two or more subjects who experience the same or similar grade 3 or higher unsolicited adverse event that is assessed as at least possibly related to the treatment
- Any Suspected Unexpected Serious Adverse Reaction (SUSAR) (considered by the Sponsor to be possibly or probably related to treatment)
- Any death or life-threatening SAE regardless of relationship to vaccine
- Any type 1 acute myocardial infarction

Dosing may be resumed following review of available safety data by the DMC, as specified in the DMC Charter.

8.3 Injection Site Reactions

Injection-site reactions are expected to spontaneously subside. Local pruritus and pain can be treated with oral medications. If significant symptoms of pain and induration persist for more than 12 hours, an ice pack may be applied locally for 30 minutes every 2 hours, as needed. Use of an ice pack prior to 12 hours after the onset of symptoms is discouraged, as it may interfere with the action of the study vaccine. Do not inject into a site if local pain, tenderness, swelling, or pruritus persist from a previous injection or other cause.

8.4 Observation Period After Study Vaccine Injection

Subjects will be observed for safety for a minimum of 30 minutes after each study vaccine injection. See [Section 10.0](#) for reporting of adverse events.

8.5 Other Supportive Care

Subjects should receive appropriate supportive care measures as deemed necessary by the investigator. The investigator should ensure that adequate medical care is provided to a subject for any adverse events (AEs) related to the study. For each disorder, attempts should be made to rule out other causes, which might require additional supportive care. The investigator should

inform the study medical monitor when medical care is needed for intercurrent illness(es) of which the investigator becomes aware.

An unscheduled visit (UNS) should be performed if there are suspected subject safety concerns. All supportive therapies will be recorded in the subject's electronic case report form (eCRF).

Subjects who are discontinued from the study will complete the Early Discontinuation/EOS Visit, if possible, not earlier than 28 days following their vaccine administration.

9 STUDY PROCEDURES

9.1 Informed Consent, Screening, and Eligibility

9.1.1 Informed Consent

The investigator or designee must review the informed consent form (ICF) with each prospective subject to be certain that the prospective subject understands the procedures and risks of the study. Prospective subjects who wish to participate in the study must provide written informed consent by signing the ICF before undergoing any screening procedures.

The information from the consent form should be translated and communicated to the subject in language understandable to the subject and/or legal representative.

A copy of the signed and dated consent form should be offered to the subject or subject's legally acceptable representative before participation in the study. The subject or his/her legally acceptable representative should be informed in a timely manner if new information becomes available that may be relevant to the subject's willingness to continue participation in the study. The communication of this information should be documented.

The investigator or designee will maintain a log of all subjects who sign the ICF. At a minimum, the log will include a subject identifier, the dates of informed consent and screening procedures, the outcome of the screening, and, if a screen failure, the reason the subject did not enroll in the study. Other items that will be collected on consented participants are age, sex, ethnicity and race. These will be captured in the study database.

Additional requirements for informed consent are presented in [Section 13.2](#).

9.1.2 Screening and Eligibility

After written consent is obtained, screening procedures must be carried out per the Schedule of Events ([Appendix 1](#)). Subjects who fail screening may not be rescreened. Subjects may have the screening window extended an additional 7-calendar days if they have equivocal laboratory results or if they cannot be enrolled during the screening window. The screening window may only be extended one time and must have prior approval by the sponsor's medical monitor. A subject must meet all of the inclusion criteria and none of the exclusion criteria to be eligible to participate in the study ([Section 5.0](#)). Documentation to support a subject's eligibility must be in the study records.

9.1.3 Demographics and Medical and Medication History

Demographic and baseline characteristics of sex, race, ethnicity, age, weight, and height of the subject will be collected.

Medical history includes clinically significant diseases and surgeries. Concomitant medications ([Section 7.5](#)) used by the subject within 28 days prior to Day 1 of the study will be recorded.

9.2 Study Visits

Procedures should be performed as close to the scheduled time as possible. A detailed outline of all scheduled study procedures is provided in the Schedule of Events ([Appendix 1](#)).

The exact time at which a procedure is performed should be recorded in the subject's study records or appropriate worksheet (if applicable).

Blood collection must be performed prior to administration of the study vaccine on each vaccine administration day.

An Unscheduled (UNS) Visit ([Section 9.5](#)) should be performed if there are suspected subject safety concerns. All supportive therapies will be recorded in the subject's CRF.

All subjects should be followed for at least 28 days after the last study vaccine injection ([Section 9.6](#)).

9.3 Immunogenicity Assessments

All immunogenicity assessments will be performed in a blinded manner in participating laboratories.

9.3.1 Antibodies to rF1V

Serum samples will be obtained to measure antibodies against rF1V. On vaccine days, samples will be collected prior to administration of study vaccine. Standardized [REDACTED] will be used to determine serum concentrations of antibodies to rF1V.

9.4 Safety Assessments

The measures of safety in the study are routine clinical and laboratory procedures. Safety will be assessed by the reporting and analysis of post-injection reactions (PIRs), AEs, SAEs, AESIs, and deaths ([Section 10.0](#)). The safety assessments are described below. The timing for Safety Assessments is provided in the Schedule of Events ([Appendix 1](#)).

9.4.1 Vital Signs

Vital signs will include oral temperature and measurements of heart rate, respiratory rate, systolic and diastolic blood pressure. Vital signs taken at the Day 1, Day 29, and Day 183 visits will be measured prior to study vaccine administration.

Vital signs will be recorded as indicated in the Schedule of Events ([Appendix 1](#)).

9.4.2 Physical Examinations

The investigator or qualified designee will conduct physical examinations. A complete physical examination is conducted at Screening. A symptom-directed physical exam at all other timepoints as outlined in [Appendix 1](#).

9.4.3 Laboratory Assessments

Laboratory assessments are listed below and will be performed according to the Schedule of Events (Appendix 1). Sample collections will be prior to administration of the study vaccine on injection days.

- HIV, HBV, HCV testing at Screening Visit
- Pregnancy testing: For female of childbearing potential (ie, onset of menarche), a serum pregnancy test will be performed at screening and must be negative for the subject to participate. Additionally, a urine pregnancy test will be performed within 24 hours prior to administration of each study vaccine and must be negative for the subject to receive study injection.
- Chemistry Panel: sodium, potassium, chloride, bicarbonate, blood urea nitrogen (BUN), creatinine, glucose, calcium, aspartate transaminase (AST), alanine transaminase (ALT), lactate dehydrogenase (LDH), bilirubin, alkaline phosphatase
- Hematology: red blood cell count, hemoglobin, hematocrit, white blood cell count with differential, and platelet count
- Reserve serum aliquot specimens will be collected and stored frozen at a central location for possible future testing

Additional details for collection and processing of laboratory samples are provided in the Laboratory Manual.

9.4.4 Post-Injection Reaction Assessments

Assessments of PIRs ([Section 10.2](#)) will be collected for a minimum of 30 minutes following each study injection at the clinical site.

On Day [REDACTED] subjects will be asked to complete an e-diary (or equivalent) to record any solicited local (pain, redness, pruritus [itchiness], and swelling at the injection site) and solicited systemic signs and symptoms (fatigue, temperature, chills, malaise, myalgia, gastrointestinal symptoms, and headache) during the 7-day follow-up period after vaccination. The severity of the post-injection reactions will be graded using the Toxicity Grading Scale for Healthy Adult and Adolescent Volunteers Enrolled in Preventive Vaccine Clinical Trials ([Appendix 2](#)).

PIRs persisting beyond 7 days after each study injection are considered AEs and should be recorded and reported as AEs. These will be included in the electronic data capture (EDC) AE dataset.

PIRs inadequately recorded by the subject in the e-diary and occurring during the diary period from Day 1 through Day 7 following each study injection can be reconstructed by the investigator in the AE CRF page. These will be included in the EDC AE dataset.

Refer to the eCRF completion guidelines for additional details.

9.4.5 Adverse Events

All AEs, as defined in [Section 10.0](#), will be evaluated and reported from immediately after the study vaccine injection on Day 1 through EOS (Week 56 or Early Discontinuation) Visit. See the Schedule of Events ([Appendix 1](#)) for the AEs collection schedule.

9.4.5.1 Serious Adverse Events

All SAEs, as defined in [Section 10.7.1](#), whether assessed as related or not related to study vaccine injection, will be evaluated from the time the consent is signed through completion of the subject's participation in the study (EOS Visit). Any SAE must be reported to Dynavax or its designee within 24 hours of knowledge of the event.

If the SAE is assessed as possibly or probably related to study treatment, it must be followed until it is considered stable or resolved, including beyond the EOS Visit.

Any SAE assessed as not related to study treatment will be followed as clinically indicated until its resolution or, if non-resolving, until it is considered chronic or stable, or until study completion (EOS Visit).

9.4.5.1.1 Type 1 Acute Myocardial Infarction (AMI)

SAEs of myocardial infarction will be further classified as Type 1 AMI if they meet the following criteria ([Thygesen, Alpert et al. 2018](#)):

- Detection of a rise and/or fall of cardiac troponin (cTn) values with at least 1 value above the 99th percentile upper reference limit and at least 1 of the following:
 - Symptoms of acute myocardial ischemia
 - New ischemic ECG changes
 - Development of pathological Q waves
 - Imaging evidence of new loss of viable myocardium or new regional wall motion abnormality in a pattern consistent with an ischemic etiology
 - Identification of a coronary thrombus by angiography including intracoronary imaging or by autopsy

9.4.6 Concomitant Medications

All concomitant medications must be recorded in the subject's CRF according to [Section 7.5](#) and per the Schedule of Events (Appendix 1).

9.5 Unscheduled Visit for Safety

An UNS Visit should be performed if there are suspected subject safety concerns. Procedures for the visit will depend on the reason for visit as determined by the treating principal investigator or sub-investigator. If an UNS Visit is performed because of a safety concern related to study treatments, at a minimum, the following should be performed:

- A targeted physical examination based on subject-reported symptoms including measurement of vital signs (heart rate, blood pressure, respiratory rate, and temperature). For additional details, see [Section 9.4.1](#) and [Section 9.4.2](#).

9.6 Duration of Follow-up

All subjects should be followed for at least 28 days after administration of the study vaccine. If a subject is discontinued early from the study, an Early Discontinuation/EOS assessment should be conducted not earlier than 28 days after the last administration of study vaccine ([Section 9.7](#)).

9.7 Early Discontinuation/End of Study

An EOS Assessment is required at Week 56 (Day 393) in alignment with the protocol, GCP as defined in International Council for Harmonisation (ICH) guidelines and US Code of Federal Regulations (CFR), and applicable local regulatory requirements. The EOS procedures will be performed as an Early Discontinuation assessment at least 28 days after the last study injection if the subject is permanently discontinued early from the trial. Investigators are responsible for monitoring the safety of subjects throughout the course of the study and for providing appropriate medical care. The investigator will perform all tasks directly or is responsible for overseeing and training qualified site personnel as delegated to perform study tasks. In addition, investigators are responsible for alerting Dynavax to any event that seems unusual and for reporting all AEs, SAEs, pregnancies, and deaths in the appropriate CRFs.

10 ADVERSE EVENTS

10.1 Definition of Adverse Events

An AE is any untoward medical occurrence associated with the use of a drug, whether or not considered drug related. An AE can therefore be any unfavorable and unintended sign (including a clinically significant abnormal laboratory finding), symptom, or disease temporally associated with the use of a medicinal (investigational) product, whether or not related to the study treatment.

Medical conditions present at Screening (ie, before informed consent is obtained) or present before the study vaccine injection (Day 1) are not AEs and are not recorded on the AE CRF. These medical conditions should be adequately documented on the Medical History CRFs. Any increase in severity or frequency of a medical condition documented as medical history after the study vaccine injection will be recorded as an AE and will be captured on the AE CRF.

Post-injection reactions ([Section 10.2](#)) persisting beyond 7 days after each study injection are considered to be AEs and need to be recorded and reported as AEs. These will be included in the electronic data capture (EDC) AE dataset.

If a PIR is inadequately recorded by the subject in the e-diary and occurred during the diary period from Day 1 through Day 7 following each study injection, the investigator can retrospectively evaluate and report at their discretion (as a health care provider), as necessary, through the date of onset on the AE CRF page. These data will be included in the EDC AE dataset.

An uncomplicated pregnancy is not an AE or SAE and should not be reported as an AE/SAE. Subjects should be followed as described in [Section 10.9](#).

The reporting period for all non-serious AEs begins at the time of the first study vaccine injection (Day 1) through EOS. All AEs will be captured on the AE CRF.

The investigator will follow all related non-serious AEs observed during the study until the AEs are considered resolved or until EOS. Dynavax or the Dynavax designee may request additional follow-up on specific unresolved events.

AEs should be documented in terms of a single medical diagnosis. When this is not possible, the AE should be documented in terms of signs and/or symptoms observed by the investigator or reported by the subject.

Any Grade 3 (severe) solicited or unsolicited AE that is considered possibly or probably related to treatment must be reported to Dynavax or its designee within 24 hours of investigator awareness of the event.

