- Grade 4 post-injection reaction (PIR) within 7 days after any study injection
- Clinically significant Grade 3 or higher systemic reaction (eg, angioedema, generalized urticaria) within 7 days after any study injection
- Grade 3 or 4 hypotension within 24 hours of any study injection
- Grade 3 or 4 respiratory reaction or symptoms occurring within 24 hours of any study injection
- Any life-threatening AE, regardless of relationship to study drug
- Any AMI
- Any confirmed immune-mediated AE
- Violation of protocol eligibility criteria
- Subject received prohibited medications
- SAE assessed as a suspected adverse reaction (SAR) or adverse reaction (AR)
- Subject becomes pregnant or begins breastfeeding

If the subject is not eligible for subsequent study injections, **the subject will not be withdrawn from the study**, but, if possible, will be followed for safety through End-of-Study (EOS) Visit.

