10.9 Serious Adverse Events

10.9.1 Definition of Serious Adverse Events

An AE is considered an SAE if it meets any of the following criteria:

- Results in death
- Is life-threatening

Note: An AE or SAR is considered *life-threatening* if, in the view of either the investigator or sponsor, its occurrence places the subject at immediate risk of death. It does not include an AE or SAR that, had it occurred in a more severe form, might have caused death.

- Requires in-patient hospitalization or prolongs existing hospitalization
- Results in persistent or significant disability or incapacity

That is, the event severely or permanently disrupts the subject's ability to perform normal life functions or daily activities.

- Results in a congenital anomaly or birth defect
- Is medically significant (Important Medical Event)

Medical and scientific judgment should be exercised in deciding whether SAE reporting is appropriate in other situations, such as important medical events that may not be immediately life-threatening or result in death or hospitalization but may jeopardize the subject. Examples of such events are allergic bronchospasm requiring treatment in an emergency room, serious blood dyscrasias, or seizures/convulsions that do not result in hospitalization. The development of drug dependence or drug abuse would also be examples of important medical events.

Note: Elective surgery is not an SAE. Additionally, an Emergency Room visit does not fulfill the criteria of hospitalization by definition of an SAE.

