10.9.2 Serious Adverse Event Reporting Requirements

Any SAEs, including serious imAESIs, that occur from the time of signed consent through the EOS Visit, whether or not the SAE is related to the study vaccine **must be reported to Dynavax or its designee within 24 hours of investigator awareness of the event**. The contact information for reporting SAEs will be provided to each site. General SAE reporting instructions are as follows:

- Submit SAE documents according to instructions provided.
- Record all SAEs on the AE CRF.
- For SAEs, record the primary event on the AE CRF; describe events occurring secondary to that primary event on the SAE form in the narrative description of the case.
- Death is an outcome, not an event. Record the event that resulted in the death as the fatal event on the AE CRF.
- For hospitalizations for surgical or diagnostic procedures, record the illness leading to the surgical or diagnostic procedure as the SAE, not the procedure itself. Capture the procedure in the narrative as part of the action taken in response to the illness.
- Elective hospitalizations will not be considered SAEs and do not need to be reported. Complications that prolong elective hospitalizations should be recorded as SAEs. Emergency room visits of less than 24 hours do not meet the criterion of hospitalization for SAE reporting purposes.

The SAE report should contain, at a minimum, the following information:

- Subject identifiers (ie, subject number)
- Suspected medicinal product
- AE term (must be listed as serious)
- Contact information for person reporting event

The relationship of the SAE to study vaccine will be assessed by the investigator (Section 10.2). Follow-up information should be actively sought and submitted as it becomes available.

The investigator will assess relationship to study treatment. In addition, the sponsor will assess relationship to study treatment and determine expectedness to study vaccine based on the current study vaccine Investigator's Brochure and USPI. The sponsor will report all study vaccine suspected unexpected serious adverse reactions (SUSARs) to regulatory authorities as expedited reports in accordance with applicable regulatory requirements (eg, 21 CFR 312.32[c] and 314.80[e] in the US). All other SAEs will be reported as part of regulatory safety updates, as required, such as in annual reports.

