10.10 Adverse Event Severity and Relationship to Study Treatment

10.10.1 Severity Grading of Adverse Events and Abnormal Laboratory Test Results

The severity of AEs and laboratory abnormalities will be graded based on the United States Food and Drug Administration's (FDA) Guidance for Industry: Center for Biologics Evaluation and Research (CBER) Toxicity Grading Scale for Healthy Adult and Adolescent Volunteers Enrolled in Preventive Vaccine Clinical Trials in [Appendix 2](#), with the modification that, by convention, all fatal AEs will be graded as Grade 5 (Fatal).

All AEs not listed in the CBER toxicity grading scale will be graded as shown in [Table 10-1](#).

Table 10-1: Grading Scale for Adverse Events Not Included in the CBER Guidance on Toxicity Grading for Healthy Volunteers in Vaccine Clinical Trials

AE Severity	Definition
Grade 1 – Mild	No interference with activity
Grade 2 – Moderate	Some interference with activity, not requiring medical intervention
Grade 3 – Severe	Prevents daily activity and requires medical intervention
Grade 4 – Potentially life-threatening	Emergency room visit or hospitalization
Grade 5	Death

CBER = Center for Biologics Evaluation and Research.

For all AEs and SAEs, if there is a change in the severity after the event onset, the event should be reported as a single entry with the maximum severity grading captured.

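### The 24-hour report in Protocol 10.1 names related Grade 3 AEs only, while the 8.2 pause rule counts Grade 3 or higher, so a narrow class of related Grade 4 events has no mandatory expedited report

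*Protocol*

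**What the plan says.** Protocol Section 10.1 sets the expedited rule for severe related events: "Any Grade 3 (severe) solicited or unsolicited AE that is considered possibly or probably related to treatment must be reported to Dynavax". The deadline for that report is "within 24 hours of investigator awareness of the event". The rule names Grade 3 and stops there.

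Section 8.2, repeated in the synopsis, temporarily stops dosing of all subjects on several triggers. One is "Two or more subjects who experience the same or similar grade 3 or higher unsolicited adverse event", where the event is at least possibly related to treatment.

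For AEs that are not on the CBER toxicity scale, Table 10-1 in Section 10.10.1 defines Grade 4 as "Emergency room visit or hospitalization". The general illness row of Appendix 2 uses the same test.

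On seriousness, Section 10.9.1 states that "an Emergency Room visit does not fulfill the criteria of hospitalization by definition of an SAE". Section 10.9.2 states: "Emergency room visits of less than 24 hours do not meet the criterion of hospitalization for SAE reporting purposes".

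Section 5.3 contains a second 24-hour notification, tied to stopping further injections in an individual subject. Its list opens with "Grade 4 post-injection reaction (PIR) within 7 days after any study injection" and continues with other defined categories.

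**The concern.** The reporting rule that should feed the pause rule is narrower than the pause rule. The two agree on relatedness, because Table 10-2 has only three levels and both rules take possibly and probably related events. They differ on grade: Section 8.2 includes Grade 4 and Section 10.1 does not mention it.

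Two subjects are enough to trigger the pause, so each qualifying event is half of the trigger, and its value depends on the sponsor hearing of each one promptly. The scheduled DMC reviews look only at the period after the first dose in Part 1 (72 hours in the first 6 subjects, 14 days in the first 18). Other reviews are as needed. In Part 2, with about 140 subjects, detection leans largely on site reporting. If a qualifying Grade 4 event reaches the sponsor more slowly than a Grade 3 event would, a pause could be recognised late while injections are still being given.

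**Working it through.** There is no figure in the plan to reproduce, and no arithmetic settles the point. The check is to take one test event and follow it through every route by which the sponsor must or should hear of it.

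**Test event.** An unsolicited AE that is possibly related, arises for example on day 12 after an injection, is treated in the emergency room for under 24 hours, and leads to no admission and no immediate risk of death.

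**Step 1: its grade.** If the event is not listed on the CBER scale, Table 10-1 makes it Grade 4 on the emergency-room visit alone. Grade 3 is a separate row with its own definition. Section 10.10.1 records one entry per event at its maximum grade, so the entry is Grade 4.

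**Step 2: does it count toward the pause?** Yes. It is unsolicited, Grade 3 or higher, and at least possibly related (Section 8.2).

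**Step 3: which reporting route catches it?**

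| Route | Timed? | Does it catch the test event? |
|---|---|---|
| 10.1, related severe AE | 24 hours | No. It names Grade 3 only |
| 9.4.5.1 and 10.9.2, SAE by hospitalization | 24 hours | No. The visit is not hospitalization under 10.9.1 or 10.9.2 |
| SAE as life-threatening | 24 hours | No. 10.9.1 requires immediate risk of death, which is narrower than the Grade 4 label of potentially life-threatening |
| SAE as an important medical event | 24 hours | Only if the investigator judges it so |
| 5.3, Grade 4 post-injection reaction or clinically significant Grade 3 or higher systemic reaction | 24 hours | No. Limited to 7 days after injection |
| 5.3, hypotension or respiratory event | 24 hours | No. Limited to onset within 24 hours of injection |
| 5.3, life-threatening AE, AMI, confirmed immune-mediated AE, related SAE | 24 hours | No, on the facts assumed |
| 8.5, tell the medical monitor when care is needed for intercurrent illness | No limit | Probably |
| 9.7, alert the sponsor to unusual events | No limit | Possibly |
| 10.1, AE form | No deadline given in 10.1 | Yes |

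**Result.** The event counts under Section 8.2. Its only mandatory 24-hour route is the important-medical-event judgment, and if the investigator decides against that, none remains. The same event at Grade 3 would have to be reported within 24 hours under Section 10.1.

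**Side check on wording.** Section 8.2, one item of Section 5.3 and the SAP's AE tabulations (Section 8.7) all use Grade 3 and above. Section 10.1 is the exception, which suggests a drafting omission.

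**The case against.** The strongest reply is that other routes leave little uncovered, and much of it stands.

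- Section 10.9.1 gives allergic bronchospasm treated in an emergency room as its own example of an important medical event. Emergency-room cases are therefore put to SAE judgment, and many will be reported within 24 hours.
- Sections 8.5 and 9.7 oblige the investigator to contact the medical monitor or sponsor in many such cases. These duties have no time limit, but they are more than data entry.
- The opening of Section 5.3 can be read as giving examples only. That reading places no clear duty on unlisted events.
- A site may well take a rule for severe related events as a minimum. The text does not say so.
- The DMC charter and the eCRF guidelines are not among the documents. How fast a non-serious Grade 4 entry reaches the sponsor cannot be judged from here.

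Three stronger readings are tempting and are not supported.

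1. A reader might infer that every emergency-room visit is Grade 4. Table 10-1 covers only AEs outside the CBER scale. In Appendix 2, fever is graded by temperature, Grade 4 redness needs necrosis or exfoliative dermatitis, Grade 4 nausea or vomiting needs hypotensive shock, and malaise has no Grade 3 or 4.
2. A reader might infer that these events go unreported. Section 10.1 puts all AEs on the AE form through the end of the study.
3. A reader might size the gap by the calendar. With doses on Days 1, 29 and 183 (Section 9.4.1), the time from day 8 after a dose to the next dose is 29 − 8 = 21 days after dose 1, and 183 − 36 = 147 days (21 weeks) after dose 2. AE collection then runs to Day 393. This is elapsed time and does not measure exposure to harm. Only related events count, and Table 10-2 ties relatedness to a reasonable temporal sequence or a known response pattern, so late events qualify less often. A pause also matters only while some subject still has a dose due.

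**Conclusion.** The mismatch between Sections 10.1 and 8.2 is real on the text, and no other mandatory 24-hour route fully closes it. The class affected is narrow. The event must be unsolicited, related, and Grade 4 by an emergency-room visit without admission. It must also not be judged medically important, not be life-threatening under Section 10.9.1, and fall outside the categories and windows of Section 5.3. For delay to matter, a same or similar event must occur in a second subject while doses remain due.

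The supported consequence is possible delay in recognising a pause trigger. The documents do not show that a pause would come late or that further subjects would be dosed as a result. They give no event rate, so the size cannot be quantified. The conclusion assumes that Section 10.1 is read as written and that no document outside the protocol and SAP already requires 24-hour reporting of non-serious Grade 4 events. This is a minor inconsistency, worth correcting because it affects a safety pause and costs almost nothing to remove.

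**What to change.** In Protocol Section 10.1, change the opening of the 24-hour rule from Any Grade 3 (severe) to Any Grade 3 or higher. The expedited report would then cover every related event that Section 8.2 counts. The change alters reporting only and leaves the pause threshold, dosing and individual discontinuation criteria as they are.

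In the same amendment, reconcile Sections 10.9.1 and 10.9.2. The first excludes any emergency-room visit from hospitalization and the second excludes only visits under 24 hours, so a longer stay is treated differently depending on which section a site reads.

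The cost is a few words in the protocol, a note in site training and a few more expedited reports.
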